**Aim 1. Examine the effects of iTBS on IC neural circuitry and task performance.**

**Hypothesis 1:** As compared to baseline: r.IFG iTBS stimulation will strengthen corticothalamic tbFC and improve IC task performance; whereas r.IFG cTBS simulation will weaken corticothalamic tbFC and result in worse IC task performance. **Behavioral analysis plan:** Following procedures outlined in C.4.a, IC performance data will be analyzed with a repeated-measures ANOVA to examine the effects of Condition (Baseline, iTBS, cTBS). **fMRI data analysis plan:** Following procedures in C.4.b—C.4.d, IC corticothalamic tbFC will be processed and modeled using our validated strategy [4] and then Fisher-transformed correlation coefficients (rZ) scores for each participant during each condition will be fed forward and analyzed in SPSS using a repeated-measures ANOVA to examine the effect of Condition.

**Aim 2. Examine the effects of iTBS on ad lib smoking.** **Hypothesis 2:** As compared to baseline: r.IFG iTBS, will extend the duration of abstinence; whereas cTBS shorten the duration of abstinence during an ad lib smoking lapse paradigm in the lab. **Behavioral analysis plan:** As in [4], time to initiate ad lib smoking during the SRT (see C.4.a.2) will be analyzed in SPSS using a repeated-measures ANOVA to examine the effect of Condition. Main effects of Condition on secondary smoking topography variables (e.g. puff volume (ml) and number of puffs) will be explored.

**Aim 3.** Examine safety and tolerability of administering r.IFG TBS. **Rationale.** Though TBS has a good safety profile [36, 37], prior studies assessment of tolerability and adverse events (AE's) have largely confined those assessments to the day of study [37]. In addition, although the TBS stimulation parameters proposed herein are published standards, the location—r.IFG for iTBS is novel and thus both acute and protracted (24 hrs. post-stimulation) safety and tolerability profiles need to be assessed. **Hypothesis 3:** r.IFG TBS will have a similar overall adverse event profile in a TUD population as previously observed in dorsolateral prefrontal cortex TMS trials. **Assessment Plan.** Participants will be administered the ROS questionnaire (see C.9) at the beginning and end of each TBS visit, and 24hrs. post TBS. [name] will oversee participant compliance and, in the event of an AE, consult with [name] who will serve as the Program Manager for AEs. Any AEs will be recorded in an AE log. If an AE is non-serious (self-limited with no intervention needed), no further action will be necessary. However, in the case of a serious, unresolved event, an AE follow-up log will be completed and subsequent safety procedures followed (see Human Subjects Section; DSMP). Treatment-emergent AEs for all participants and

comparisons between the number of participants with any adverse events will be conducted using Pearson's chi-squared test statistic.

**Exploratory Aims.** *MRS Rationale.* Converging evidence supports changes in glutamate release as a likely molecular mechanism associated with synaptic plasticity [64]. Glutamate receptors are necessary for the initiation and expression of LTP and LTD and GABA receptors are involved in the modulation of these phenomena. Consistent with animal findings [65], proton MRS studies have demonstrated TUD is associated with abnormal medial prefrontal [66] and thalamic [67] concentrations of glutamate along with evidence for medial prefrontal GABA disturbances being associated with attentional bias to drug cues [68]. Emerging evidence suggests that LTP-like TMS to l.dIPFC is associated with increases in localized glutamate concentrations in depressed [69, 70] and healthy [71] individuals. Recent research has also demonstrated that LTD-like cTBS to motor cortex is associated with increases in localized GABA concentrations [72]. However, to the best of our knowledge, no studies have investigated the impact of TBS on r.IFG GABA or glutamate concentrations or the impact of TBS on localized neurometabolites in TUD. We posit that r.IFG TBS induced neurochemical changes may subsequently correspond with changes in IC.

[figure not shown]

Figure 3. Sample r.IFG voxel placement (top panel), sample fitted GSH (bottom-left), GABA / Glx (bottom-right) and Water / Creatine (bottom-center) spectra acquired with HERMES.

**Data acquisition:** At each visit, the MRS acquisition voxel ( $25 \times 25 \times 30 \text{ mm}^3$ ) will be placed in the r.IFG to correspond to the brain tissue directly underneath the TMS coil (Fig. 3). Following placement of 6 saturation bands parallel to the voxel faces and auto-shimming, single-voxel water-suppressed  $^1\text{H}$ -MRS spectra will be acquired via HERMES (TR=2000ms; TE=80ms; number of averages=320) using editing pulse frequencies for GABA and GSH acquisition (1.9 [ON GABA], 4.56 [ON GSH], and 7.5 ppm [OFF] [73]; and a PRESS sequence maximally sensitive to glutamate (TR=2000ms; TE=40ms; number of averages=128 [74]. Unsuppressed water spectra will be acquired for each sequence. **Data analysis:** Skull stripping and whole brain tissue-type segmentation will be performed on MP-RAGE images using FMRIB software [75]. In-house MATLAB functions will be used to extract the 3D volume corresponding to the positioned MRS voxel to obtain within-voxel gray matter (GM), white matter (WM) and cerebrospinal fluid (CSF) tissue content for each subject. GM/WM ratios will be used as covariates in all statistical analyses. Eddy currents and residual water will be removed using in-house MATLAB functions. HERMES data will be analyzed using the Gannet MATLAB toolbox [76]. PRESS data will be analyzed using LCModel 6.3 [77]. Metabolites with fitting uncertainties  $<20\%$  will be retained.

Water will be quantified from a Gaussian-Lorentzian fit to the non-water-suppressed data. Within-voxel tissue fractions of gray and white matter and cerebrospinal fluid will be calculated based on automated segmentation in SPM 12 using a volume mask generated in Gannet [78]. Metabolite concentrations will be normalized to unsuppressed water and corrected for within-voxel CSF fraction. Cramer-Rao Lower Bound (CRLB) values will be provided by the ProFit software and only estimates with CRLB values < 20% will be submitted to further analysis. Estimated metabolite peak areas will be normalized to the unsuppressed water signal. Finally, metabolite/water, along with metabolite/creatinine, ratios will be corrected for within-voxel CSF fraction [79]. Glutamate, glutamine, and GABA ratios will be entered into HLM models with a priori contrasts to examine differences in metabolite concentrations following r.IFG iTBS vs cTBS and baseline. Associations between metabolite concentrations and corticothalamic tbFC, IC and smoking on the SRT will be examined.

**Missing Data and Attrition.** Missing data in repeated-measures study designs are problematic but can be minimized by effective communication between staff and participants and minimizing participant burden via maintaining a relatively compact study duration. The study team has significant experience with ensuring a robust and unbiased approach and minimizing missing data (See C.8)

*Screening/Training Visit:* During screening, all aspects of the study will be described to participants and informed consent will be acquired. Participants will provide demographic and employment history via self-report forms. Then, participants will be asked to provide breath samples to test 1) expired carbon monoxide (CO) and 2) an estimate of blood alcohol content (BAC). Additionally, urine samples will be obtained in order to assess pregnancy status and to screen for illicit drug use. Among females, the pregnancy screen will be conducted prior to the drug screen. If the result of the pregnancy test is positive, participants will not be screened for drug use or undergo any further study procedures. The results of the drug test will be recorded primarily for data analysis purposes and cocaine will be the only exclusionary illicit substance. After biological screening is complete, participants will complete medical and smoking history, MRI safety, and contact information forms and will be verbally guided through a timeline follow-back of cigarettes and other tobacco products. Participants who meet all selection criteria will be provided with the option to continue onto the training phase of the visit. During training, participants will learn and practice the inhibitory control (IC) task and fill out commonly used questionnaires that assess state and trait mood and cognitive processes (see Appendix).

*Experimental Baseline Visit:* At this visit, participants will first: provide an expired breath CO sample in order to assess recent smoking; and, among females, provide a urine sample in which the pregnancy test must be negative. Next, breath alcohol levels will be assessed with a handheld breathalyzer and participants must record a BAL of 0.0. If participants continue to be eligible after the biological samples, they will complete study questionnaires to assess mood and to characterize smoking-related behavior. After this, participants will move on to the first fMRI scan followed by the SRT task.

*fMRI Scan:* 1) a high-resolution anatomical scan; 2) a 7-minute run of the IC task (see Fig 1); and 3) a six minute resting state BOLD (blood-oxygen-level-dependent).

*Randomization:* This will be a single blind study where participants will be randomized 1:1 to receive one session of either intermittent TBS (iTBS) or continuous TBS (cTBS) following the first fMRI.

*SRT:* The Smoking Relapse task will be administered as described above.

*Experimental Visits 1 & 2:* At the beginning of each of these experimental visits, participants will first: provide an expired breath CO sample in order to assess recent smoking; and, among females, provide a urine sample in which the pregnancy test must be negative. Next, breath alcohol levels will be assessed with a handheld breathalyzer and participants must record a BAL of 0.0. If participants continue to be eligible after the biological samples, they will complete study questionnaires to assess mood and to characterize smoking-related behavior. After this, participants will move on to the first of two fMRI sessions followed by the TMS session and the second the fMRI and SRT task.

*fMRI Scan 1:* 1) a high-resolution anatomical scan; 2) a 7-minute run of the IC task (see Fig 1); and 3) a six minute resting state BOLD (blood-oxygen-level-dependent).

*TMS:* Upon randomization, participants will receive either iTBS or cTBS per the theta burst protocols described above.

*fMRI Scan 2:* 1) a high-resolution anatomical scan; 2) a 7-minute run of the IC task (see Fig 1); and 3) a six minute resting state BOLD (blood-oxygen-level-dependent). The second

*SRT:* The Smoking Relapse task will be administered as described above.

**Analytic Strategy** Behavioral and neural data analysis strategies are found in [1] and detailed below.

*fMRI data processing.* Pre-processing of functional images includes: slice-time correction and realignment[18]; motion outlier detection (framewise displacement  $> 4$  mm ( $\sim 1$  acquisition voxel) [www.nitrc.org/projects/artifact\\_detect](http://www.nitrc.org/projects/artifact_detect)) and correction (via nearest-neighbor interpolation); despiking at 4% of global mean ([cibsr.stanford.edu/tools/human-brain-project/artrepair-software.html](http://cibsr.stanford.edu/tools/human-brain-project/artrepair-software.html)); coregistration of functional images to structural image; warping to MNI space using forward deformations, resampling to  $(1.5\text{mm})^3$  voxel size (i.e.,  $3.375\mu\text{L}$ ) and smoothing with a  $(10\text{mm})^3$  FWHM Gaussian filter.

Task-based functional connectivity (tbFC) data processing. Pre-processed fMRI data will be uploaded into the conn14 toolbox ([www.nitrc.org/projects/conn](http://www.nitrc.org/projects/conn)) for denoising and connectivity analyses. Using unsmoothed segmented tissue images, along with functionally-defined regions of interest (ROIs), significant clusters will be exported using MarsBaR ([marsbar.sourceforge.net](http://marsbar.sourceforge.net)) from the NoGocorrect - RareGocorrect ANCOVA model. Mean time-courses from the unsmoothed BOLD signal from each ROI will be characterized with no additional principal components. Confounds (mean white matter, cerebrospinal fluid signal, and motion parameters) will be regressed out of the mean signal for each ROI. A high-pass filter of 0.008 Hz will be performed after confound regression (no detrending).

*Inhibitory Control Network (ICN) Mask.* An ICN mask that was created in WFU Pickatlas ([fmri.wfubmc.edu/software/pickatlas](http://fmri.wfubmc.edu/software/pickatlas)) for previous studies, including R.IFG, bilateral thalamus, STN, preSMA and left primary motor cortex (BA 4 / M1), will be used as an explicit mask in all analyses.

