*Region of Interest (ROI) Identification.* For each subject, the IC-contrast image will be loaded into, and overlaid onto their coregistered T1, in MRIcroGL (<http://www.mccauslandcenter.sc.edu/mricrogl/>). The PI ([name]) will train a postdoctoral fellow on how to identify the peak cluster of activation in the r.IFG (e.g. neuroanatomical boundaries, software) and, once trained, work as a team to identify ROI's with >95% agreement. The IFG is comprised of three sub-divisions—Pars opercularis, Pars triangularis and Pars orbitalis—all of which have been demonstrated to play a role in inhibitory control [52]. Across our work with TUD related disruptions in IFG activation [4, 32-35], activity in the posterior-ventral aspect of the Pars triangularis and/or posterior extent of the Pars opercularis—ventral to the inferior frontal sulcus, dorsal to lateral sulcus, anterior to the precentral sulcus—is the focal extent of the r.IFG node in the corticothalamic circuit that mediates IC and smoking relapse vulnerability [4], and is sensitive to TBS modulating IC. Thus, we have clearly defined anatomical boundaries for confining the functionally defined peak cluster that will serve as the ROI for each participant. Each participant's functionally defined ROI [as shown in Fig. 2] will be used for neuronavigating TBS.

**Neuronavigation Protocol.** Following the baseline scan and ROI identification procedure, neuronavigation will be performed using the Rogue Research Inc. © Brainsight system. First, co-registered anatomical and functional ROI data will be entered into a participant’s workflow profile, followed by skin and full-brain curvilinear reconstructions, 3-landmark identifications (bridge of nose, l.ear, r.ear), placing a pin on the ROI and coil alignment with the gyrus. The same setup parameters will be used across each of the two TBS visits and I/O BOX TTL triggers enabled to record the spatial parameters for each pulse: a) distance to target; b) target error; c) angular error; and c) twist error, for use in assessing quality control and entered as nuisance covariates in statistical analyses. In our pilot study (results shown in Fig. 1), the mean target error (i.e. shortest distance from the line projecting into the head along the coil’s path) across all conditions was 2.6 mm ( $\pm 1.0$ )—within range of the manufactures recommended threshold (3mm)—for each participants ROI (samples in Fig. 2).

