*Figure 2. Individual variability in inhibitory control task-based r.IFG activation.* Randomly selected cases ( $n = 5$ ) from our pilot IC-task based fMRI-guided TBS study. Though all participants exhibited significant r.IFG activation in the IC-contrast image—similar to that reported in our prior published work [4: upper right excerpt], significant inter-subject variability in neuroanatomy along with variability in the foci of functional activation were identified above. Thus, an individual subject’s functional activity in their native space provides greater spatial specificity for targeting stimulation, as compared to using group mean activity following normalizing to an average template. *Landmarks for reference: \* = sinus; STG = Superior temporal gyrus.*

**Theta Burst Stimulation Protocols.** Following fMRI data preprocessing, modeling, ROI identification and verification (C.4.b) and setting up the neuronavigation protocol (C.4.c), participants will be randomized to receive TBS to the r.IFG on two separate experimental visits: iTBS on one visits; cTBS on one visit—counterbalanced across participants.

**Determining Resting Motor Threshold.** Standard procedures will be used to determine the participants resting motor threshold (RMT) using parameter estimation by sequential testing (PEST) procedures [53].

**Intermittent Theta Burst Stimulation (iTBS) to the r.IFG.** The total duration of the iTBS protocol [38] is 190 seconds. Participants will receive stimulation over the r.IFG (A series of 3-burst pulses presented at 5Hz, 10 pulses/sec, 10 pulses/train, 20 trains, 10.0 sec intertrain interval; 80% RMT, MagPro) using a figure 8 coil (Coil Cool B65 A/P). This protocol has been shown to enhance IC performance as shown in Figure 1.

**Continuous Theta Burst Stimulation (cTBS) to the r.IFG.** The total duration of the cTBS protocol [41] is 34 seconds. Participants will receive stimulation over the r.IFG (An intermittent series of 3-burst pulses presented at 6Hz, 18 pulses/sec, 600 pulses/train, .1 sec intertrain interval; 80% RMT, MagPro) using a figure 8 coil (Coil Cool B65 A/P). This protocol has been shown to reduced IC performance as shown in Figure 1.

**Randomization and Blinding.** This study utilizes a double-blind, crossover design with a counterbalanced (latin-square) [62] TBS condition order. Given the short—~1hr duration of the

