## **X. Compensation**

Participants will receive up to \$285 total in cash over one screening/training visit and three experimental visits (total study visits = 4): \$55 at the training visit, \$50 for each of three fMRI session-visits (\$150 total: baseline, TMS v1, TMS v2), \$25 for each of two TMS session-visits (\$50 total: TMS v1, TMS v2), up to \$10 for performance on the SRT on each of three experimental visits (\$30 total).

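### Baseline is always the first experimental visit, so the Aim 1 and Aim 2 ANOVAs confound visit effects with TBS, and the randomised iTBS-versus-cTBS contrast is not pre-specified

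*Combined protocol and SAP*

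**What the plan says.** Section VII, Aim 1, states that "IC performance data will be analyzed with a repeated-measures ANOVA to examine the effects of Condition (Baseline, iTBS, cTBS". The Fisher-transformed corticothalamic correlations (rZ) are analysed the same way. For Aim 2, "time to initiate ad lib smoking during the SRT (see C.4.a.2) will be analyzed in SPSS using a repeated-measures ANOVA". None of these three analyses has a visit, period or sequence term, and none names a contrast. The hypotheses are framed against Baseline; Hypothesis 2, for example, reads "As compared to baseline: r.IFG iTBS, will extend the duration of abstinence".

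The visit order is fixed by design. Under Neuronavigation Protocol, "Following the baseline scan and ROI identification procedure, neuronavigation will be performed", so the target cannot exist until the baseline scan is done. Section X lists the visits as "baseline, TMS v1, TMS v2". Randomisation covers only the two stimulation visits: "participants will be randomized to receive TBS to the r.IFG on two separate experimental visits", with order counterbalanced.

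The visits also differ in content. At the Experimental Baseline Visit, "After this, participants will move on to the first fMRI scan followed by the SRT task". At Experimental Visits 1 & 2, "participants will move on to the first of two fMRI sessions followed by the TMS session and the second the fMRI and SRT task".

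**The concern.** Baseline is a level of the analysed factor but was never part of the randomisation. It differs from the TBS levels in three ways besides stimulation: it is always first, it comes earlier in the participant's exposure to the tasks, and its SRT follows a shorter session. A model with Condition as its only factor cannot separate these from TBS.

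A common shift could make the omnibus F or one Baseline contrast significant with no TBS effect. It could also hide one true effect while enlarging the other. The opening of Section VII says milestones on iTBS against cTBS and baseline must be met before UH3, but gives no test. An effect on that decision is therefore possible but not established.

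**Working it through.** **1. Is iTBS versus cTBS tested elsewhere for these outcomes?** No. Statistical Analyses specifies an iTBS-versus-cTBS ANCOVA, but defines its outcome as the BOLD contrast and expressly separates it from IC accuracy. The spectroscopy section has a priori contrasts, for metabolites only. The tbFC paragraph names no contrast. The neuronavigation covariates exist only at TBS visits and do not model period.

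**2. Exposure by schedule.** With one training run, the Baseline IC run is the 2nd and the post-TBS runs are the 4th and 6th, because each TBS visit also has a pre-TBS run. The SRT is performed for the 1st time at Baseline, then for the 2nd and 3rd.

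**3. What each comparison estimates.** Let τi and τc be the TBS effects, and p2 and p3 the shifts at the two TBS visits relative to the baseline visit. With balanced order:

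- E[iTBS − Baseline] = τi + (p2 + p3)/2
- E[cTBS − Baseline] = τc + (p2 + p3)/2
- E[iTBS − cTBS] = τi − τc

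Both Baseline contrasts carry the same bias and the randomised contrast carries none. This holds whatever the size of the shift.

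**4. Size, continuous outcomes (IC accuracy, rZ).** The plan gives no power figure or visit-effect size to reproduce. From the plan: 30 usable datasets (Section VI) and alpha .05. Assumed: two-sided tests, total SD 1, within-person correlation ρ of 0.5 or 0.7, and a common shift s at both TBS visits. With no TBS effect the condition means are 0, s, s, and the omnibus F(2, 58) has noncentrality λ = 30 × (2s²/3)/(1 − ρ). For s = 0.3 and ρ = 0.5, λ = 30 × 0.06/0.5 = 3.6.

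| s (SD) | λ, ρ = 0.5 | F rejects | λ, ρ = 0.7 | F rejects |
|---|---|---|---|---|
| 0 | 0 | 5% | 0 | 5% |
| 0.2 | 1.6 | 18% | 2.67 | 28% |
| 0.3 | 3.6 | 36% | 6.0 | 56% |
| 0.5 | 10.0 | 79% | 16.67 | 95% |

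Simulation (20,000 runs per scenario) agrees. In the same runs iTBS versus cTBS stays at about 5%, and the full Hypothesis 1 pattern appears in under 0.01%.

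**5. Masking.** Take true effects of +0.3 SD (iTBS) and −0.3 SD (cTBS). The SD of a paired difference is √(2(1 − ρ)), so the noncentrality for cTBS versus Baseline is 0.3 × √30/√(2(1 − ρ)): 1.64 at ρ = 0.5 and 2.12 at ρ = 0.7. Power is 36% and 54%. A common gain of 0.3 SD makes the expected difference −0.3 + 0.3 = 0, and power in the hypothesised direction falls to 2.5%. iTBS versus cTBS still differs by 0.6 SD, with power 89% and 98%. A 0.3 SD loss would hide the iTBS contrast instead.

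**6. SRT time.** This was simulated in six-minute blocks capped at 60 minutes, with assumed latent mean/SD of 30/20 minutes (about 12% of sessions at the cap) or 50/25 (about 44%). With no TBS effect and shifts of 0 / 0.2 / 0.3 / 0.5 SD, the omnibus F rejects as follows:

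- Light cap: 5 / 17 / 33 / 75% (latent correlation 0.5) or 5 / 24 / 50 / 92% (0.7).
- Heavy cap: 5 / 14 / 26 / 59% (0.5) or 5 / 19 / 38 / 79% (0.7).

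iTBS versus cTBS stays at about 5%. In the masking scenario at correlation 0.5, power for cTBS below Baseline falls from 33% (light) or 28% (heavy) to 2.5%. Power for iTBS versus cTBS moves from 86% to 84% (light) or from 77% to 70% (heavy).

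**7. Why a period term.** If completers split 18/12 by order and the second TBS visit is 0.3 SD higher than the first, the unadjusted iTBS − cTBS estimate is off by 0.3 × (18 − 12)/30 = 0.06 SD, in a direction set by the larger order group. Power for a 0.4 SD difference (ρ = 0.5) is then 41% unadjusted against 55% adjusted, or 65% against 54% in the mirror split. Unadjusted type I error is 5% at 18/12 and 7% at 20/10; adjusted, it is 5%. If 10 of 40 (20 per order) are lost at random, a split of 18/12 or worse has probability 6.5%.

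**The case against.** The best counter-argument is that the hypotheses predict opposite directions from Baseline, and a common shift cannot produce that. This is right. It limits the false-positive risk to a reading based on the omnibus F or one contrast. But the omnibus effect of Condition is the only test these analysis plans name, and masking is not answered. The 2.5% masking figure does depend on setting the shift equal to the true effect, so that they cancel exactly.

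Second, the 12-person pilot in Section I offers a possible anchor. If its effects (D = .81 and .5) were truly equal and opposite, the common component would be (0.81 − 0.50)/2 = 0.155. Treating that as a shift in SD units gives an omnibus rate of about 12% (ρ = 0.5) or 18% (ρ = 0.7), well below the larger scenarios. The symmetry is assumed and D is not defined, so this does not settle the size. It does show that the shift may be modest.

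Third, the task training, mock scanner and practice with the smoking device are meant to reduce novelty at the first visit, and may well do so. They cannot equalise visit order or session length.

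Fourth, the longer TBS visit is set out only in the Experimental Visits 1 & 2 text; the summaries in Sections VII and XII mention just the repeat after TBS. The summaries are consistent with the detailed schedule, and the visit-order problem stands without the visit-length one.

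Last, the plan names no contrasts at all for these outcomes, and those with Baseline are inferred from the hypotheses. That is a reason to name them.

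**Conclusion.** The concern holds. For IC accuracy, corticothalamic rZ and SRT time, the omnibus F and both Baseline contrasts mix TBS with visit order, practice and session length, and the one contrast that randomisation protects is not pre-specified. That conclusion needs no assumed numbers.

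The size does. The direction of the net shift is unknown and it could be zero. Assumed shifts of 0.2 to 0.5 SD raise the omnibus rejection rate from 5% to between 18% and 95% for the continuous outcomes, and to between 14% and 92% for SRT time. These are sensitivity figures, not estimates of what will happen. The plan should be changed on this point, but the design is not invalidated, because the randomised comparison is available in the data already planned.

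**What to change.** In the Aim 1 and Aim 2 analysis plans:

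- Pre-specify iTBS versus cTBS on the post-TBS outcome, with a period term, as the key contrast for IC accuracy, corticothalamic rZ and SRT time.
- Keep the Baseline comparisons in Hypotheses 1 and 2 as supportive, labelled as confounded with visit order and visit length.
- State that neither the omnibus F nor a single Baseline contrast alone establishes a TBS effect.
- Optionally, for IC accuracy and rZ, use the same-visit pre-TBS run as a covariate or show pre-to-post change by condition, after confirming that the design summaries in Sections VII and XII are meant to include that scan. No pre-TBS SRT is described, so this is not available for SRT time.

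This changes analysis text only and needs no new data. The period term uses one degree of freedom; it is there to remove bias, and at a 15/15 split it makes little difference to power (53% unadjusted, 56% adjusted in the scenario above). The real cost is interpretive: iTBS versus cTBS does not show which stimulation acted, since a harmful cTBS effect alone could make it significant. Direction relative to Baseline would still rest on the supportive comparisons.

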## VII. Study Procedures and Research Design

The UG3 phase is a proof-of-concept study to test mechanistic hypotheses of the acute effects of TBS on corticothalamic inhibitory control (IC) task-based functional connectivity (tbFC), IC task performance and ad lib smoking in the laboratory while preliminarily evaluating safety and tolerability of TBS among individuals with TUD. Clearly defined milestones, focused on iTBS

versus cTBS and baseline on IC circuitry, will be met before proceeding to Phase 2 (UH3), a 4-session (over 2-weeks) randomized iTBS versus cTBS trial to assess smoking behavior over two-weeks post-treatment period.

As shown in Fig. 1, individuals ( $N=30$ ) with TUD will complete a baseline MRI visit and, using a crossover design, be randomly assigned to receive iTBS on one visit and cTBS on the other visit. Following TBS, they will repeat the protocol and then perform the SRT [4]. The effects of TBS on IC brain and behavior and smoking on the SRT, along with safety and tolerability, will be assessed.

**Strategies to Ensure a Robust and Unbiased Approach.** As detailed throughout this section, the proposed study will achieve robust and unbiased results via several design features including: explicit inclusion/exclusion criteria; randomization and blinding; use of validated measures; explicit hypotheses and well-validated analytic strategies; power estimates; and careful consideration of potential confounds. As standard practice in our laboratory, we will maximize participant retention and data collection compliance, while maximizing fidelity by providing participants with training on all task procedures prior to data collection.

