effects of a single session of TBS on neural function and behavior [38, 41], a crossover design with a minimum of a 2-day washout period between TBS session is appropriate for this study [63]. Both the participants and the research technicians, other than the technician administering TBS, will be blinded to the condition order. At the end of each visit, the participant and the researcher will independently complete a form indicating which TBS condition they believe was administered during the session and provide a confidence rating on a scale from 1-10.

**Hypothesis Testing.** All hypothesis testing will be conducted with  $\alpha < .05$ , unless otherwise noted. **Rationale.** Based upon the tenet that iTBS induces LTP and strengthens network activity, our prior published work demonstrating that corticothalamic tbFC mediates the association between successful IC task performance and inhibiting smoking [4], and our pilot data demonstrating r.IFG iTBS improves IC (Fig. 1), we hypothesize that r.IFG iTBS will strengthen corticothalamic tbFC, improve IC and attenuate smoking lapse/relapse.

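### Directional, two-part hypotheses for Aims 1 and 2 are tested only by a Condition effect that shows neither direction nor which protocol acted; pre-specify signed contrasts.

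*Combined protocol and SAP*

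**What the plan says.** Section VII of the combined protocol and SAP, under Aim 1, states Hypothesis 1 in two parts, both relative to baseline: "r.IFG iTBS stimulation will strengthen corticothalamic tbFC and improve IC task performance", while "r.IFG cTBS simulation will weaken corticothalamic tbFC and result in worse IC task performance". Hypothesis 2 has the same form for time to smoke on the SRT: longer after iTBS, shorter after cTBS.

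The named tests are:
- IC performance: "IC performance data will be analyzed with a repeated-measures ANOVA to examine the effects of Condition (Baseline, iTBS, cTBS".
- tbFC: Fisher-transformed scores are "fed forward and analyzed in SPSS using a repeated-measures ANOVA to examine the effect of Condition".
- SRT time (Aim 2): it "will be analyzed in SPSS using a repeated-measures ANOVA to examine the effect of Condition".

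The Hypothesis Testing paragraph ("All hypothesis testing will be conducted with" alpha below .05) adds no contrast, sidedness or decision rule. Planned comparisons appear only under Exploratory Aims, where the spectroscopy metabolites go into "HLM models with a priori contrasts". The Statistical Analyses subsection adds an iTBS vs cTBS ANCOVA on the BOLD inhibitory-control contrast, which it explicitly separates from IC accuracy. The tbFC paragraph after it names no comparison.

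On use of the results, the opening of section VII says that milestones on iTBS "versus cTBS and baseline on IC circuitry, will be met before proceeding to Phase 2 (UH3"). The IC task paragraph says the task will inform that decision. No numerical criterion is printed.

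**The concern.** A three-level Condition effect has two degrees of freedom and no sign. It responds in the same way to the hypothesised order, to the exact reverse, to both protocols moving together, and to cTBS impairment with iTBS inert. A significant result therefore does not establish either half of Hypothesis 1 or 2.

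The distinction matters because the next phase is an iTBS efficacy trial. Evidence that cTBS impairs inhibitory control is informative about mechanism, but it does not show that iTBS helps. If the signed comparisons are not fixed in advance, which pair carries the claim is left to be chosen once the data are seen.

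**Working it through.** **Inputs from the document.** 30 usable datasets from 40 enrolled (section VI). Alpha .05. Pilot effects, N=12 (section I): iTBS vs baseline D = .81, cTBS vs baseline D = .5, iTBS vs cTBS D = 1.56. Power estimates are mentioned as a design feature, but no power figure is given, so there is none to reproduce.

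**Assumptions.** Normal outcomes, equal variances and correlations across conditions, complete data. The document gives no within-person correlation (rho), so 0 to 0.7 is used. It does not say whether the pilot D is in raw-SD or paired-difference units, so both are shown. SRT time is capped at 60 minutes and recorded in six-minute blocks, so the figures are only a guide for that outcome.

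**1. Omnibus F, effects in SD of the paired difference.** Noncentral F with (2, 58) df and ncp = 2n × Σ(mean_i − grand mean)².

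| Baseline, iTBS, cTBS | Σ of squares | ncp = 60 × Σ | Significant |
|---|---|---|---|
| 0, 0, −0.5 (cTBS only) | 1/6 | 10 | 79.4% |
| 0, +0.5, +0.5 (both move together) | 1/6 | 10 | 79.4% |
| 0, +0.25, −0.25 (hypothesised order) | 0.125 | 7.5 | 66.3% |
| 0, −0.25, +0.25 (reversed order) | 0.125 | 7.5 | 66.3% |

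**2. cTBS only, effects in raw SD.** ncp = n × Σ/(1 − rho). With Σ = 1/6 this is 5/(1 − rho). At half the effect Σ is a quarter as large, so ncp = 1.25/(1 − rho).

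| rho | cTBS −0.5 | cTBS −0.25 |
|---|---|---|
| 0 | 48.2% | 15% |
| 0.30 | 64% | 20% |
| 0.5 | 79.4% | 26% |
| 0.7 | 95.5% | 41% |

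If nothing differs, the rate is the nominal 5%.

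**3. A planned iTBS vs cTBS contrast on its own.** Paired t, 29 df, two-sided .05, ncp = d × √30.
- Hypothesised order with iTBS − cTBS = 0.5: power 75.4%, against 66.3% for the F.
- At the pilot effects (.81 and −.5) the F is significant in at least 99.6% of trials, so there is almost nothing to gain.
- cTBS only at −0.5: the iTBS − cTBS difference is again 0.5, so the contrast favours iTBS in 75.4% of trials. This contrast alone does not remove the problem.

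**4. Requiring both iTBS vs cTBS and iTBS vs Baseline, each significant in favour of iTBS.**
- iTBS null, cTBS −0.5: the second contrast is null, so one tail caps the rate at 2.5%. The joint rate by simulation is about 2.4%.
- iTBS +0.5, cTBS −0.5: the first contrast (difference 1.0) is almost always significant and the second has 75.4% power, so jointly about 75%.
- iTBS +0.25, cTBS −0.25: 75.4% for the first and 26% for the second, jointly about 24%.

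**5. Session effect.** Baseline is always the first experimental visit; only the iTBS/cTBS order is randomised. If neither protocol acts but both later visits shift by an assumed +0.3 raw SD, iTBS vs Baseline alone is significant in favour of iTBS in 20%, 27%, 36% and 54% of trials for rho 0, 0.30, 0.5 and 0.7.

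**The case against.** The best defence is that follow-up comparisons after a repeated-measures ANOVA are routine. The pilot report in section I gives signed, condition-by-condition effects after its own F, so the team would presumably do the same here. Also, cTBS worsening is half of each hypothesis, so an F driven by cTBS correctly detects a Condition effect. Both statements are fair. They do not fill the gap: the plan does not say which comparisons follow, in what order, or what pattern supports an iTBS claim, although it does specify contrasts for an exploratory outcome.

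The iTBS vs cTBS ANCOVA is a genuine directional opportunity, but it concerns BOLD activation, covers none of the three hypothesised outcomes and has no baseline comparison.

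The objection that the size depends on unstated quantities stands. The 79% is one point in a wide range, and it requires cTBS to have a sizeable effect. The power argument is also limited: it disappears at the pilot effects.

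Two stronger readings are tempting and unsupported. A reader might infer that the UH3 decision rests on a significant F. The document refers to defined milestones but prints no criterion and does not link them to that test. A reader might also count nine unadjusted pairwise tests (three outcomes, three pairs) and compute an error rate as if they were independent. The plan specifies no pairwise tests, and three differences among three means cannot be independent.

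**Conclusion.** The concern holds in this form: for IC performance, tbFC and SRT time, the only named test cannot confirm the directional, two-part hypotheses it is attached to. With 30 datasets and iTBS inert, it is significant in 79% of trials if cTBS worsens by 0.5 SD of the paired difference. On a raw-SD reading of the pilot effect the range is 48.2% to 95.5%, falling to 15% to 41% at half that effect. These figures rest on the assumed correlations and on cTBS doing something, which the protocol itself predicts. The loss of power is secondary: about nine points (66.3% vs 75.4%) at a modest 0.5 SD difference, negligible at the pilot effects. The analysis can be run as written, so this is a change that should be made rather than a fatal flaw.

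**What to change.** In the Aim 1 and Aim 2 analysis plans, replace the effect of Condition as the hypothesis test with signed contrasts from the same model, each reported with an estimate and 95% CI. For each outcome:

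1. Test iTBS vs cTBS, the randomised comparison, two-sided at .05.
2. Only if that is significant in the hypothesised direction, test iTBS vs Baseline, two-sided at .05.
3. Report cTBS vs Baseline alongside.

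Claim an iTBS benefit only if steps 1 and 2 are both significant in the hypothesised direction. Where the UH3 decision uses these outcomes, base it on this rule.

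State the limit of step 2: because Baseline always comes first, that contrast can absorb a practice or session effect. Step 1 protects against a shift common to both TBS visits when cTBS is inert, but not when cTBS also impairs.

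The cost is SAP wording, with no new data or visits, and lower power for an iTBS claim than a single contrast would have: about 75% if the true effects are +0.5 and −0.5 SD of the paired difference, and about 24% if each is 0.25 SD.
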